8.1 EHR Study Cohort Creation and Longitudinal Assessment

Early in the project period, a query to describe the clinical characteristics, management, and longitudinal outcomes of patients with T2DM and CVD will be distributed to sites participating in the EHR study. Out of approximately 80 data partner (DataMart) sites, at least 15 are expected to return results for this first query. Sites that return query results are expected to be both those that do participate in the trial, as well as sites that have no further engagement. The results of this query will help establish a broad, national baseline to better understand this population and their management.

Additionally, for the EHR sites that participate in the trial, patient recruitment will be facilitated by use of a cohort identification query. This query will be programmed centrally and distributed to each site to run at desired intervals to identify patients with designated inclusion and exclusion criteria, as listed in the Patient Inclusion and Exclusion section of the Trial Summary table. Results of the cohort identification query will be utilized and remain at each site.

8.2 Query Creation, Distribution, and Return

The EHR query will be carefully created with input from the clinical and educational intervention team to include all relevant characteristics and possible management practices. While the final set of data elements will be selected by the study team based on feasibility and clinical relevance, elements of interest include (but are not limited to) the following and will be

selected from the PCORnet Common Data Model (CDM) v4.0 (see http://www.pcornet.org/pcornet-common-data-model/):

- Demographics (age, sex, race)
- Laboratory values (creatinine, hemoglobin A1C)
- Body mass index
- Blood pressure
- Comorbidities (hypertension, lipid disorders, cancer, pulmonary disease, heart failure, retinopathy, stroke/TIA, serious mental illness, atrial fibrillation)
- Medications (antithrombotics, antihypertensives, ACEI/ARB, beta blockers, calcium channel blockers, antiarrhythmics, lipid lowering medications, diuretics, oral glucocorticoids, metformin, sulfonylureas, meglitinides, thiazolidinediones, GLP-1 receptor agonists, SGLT2 inhibitors, DPP4 inhibitors).
- Inpatient and outpatient encounters within the health system, including cardiovascular and non-cardiovascular hospitalizations

Once all elements are defined, code lists comprising ICD9-10 codes and LOINC codes will be created so as to represent these elements according to the PCORnet CDM. From these code lists, the SAS-based queries will be programmed (i.e., query creation). As described below, queries are distributed to data partners via a secure file transfer system. Once received, data partners run the query locally against their standardized local data set, and then return the results of the query back for compilation (i.e., return). Data partners that are eligible to receive the baseline, descriptive query will be those that have populated the prescribing medication table according to the PCORnet CDM and have passed all relevant data quality checks during the most recent round of data curation (i.e., updating, which is conducted quarterly).

Participating EHR data partners will participate in a study cohort query in order to examine essential baseline, covariate, and outcome data to ensure they are correctly populated within the sites CDM and within acceptable boundaries of validity prior to responding to the descriptive queries. The study query package will be transmitted via a secure file transfer system which will be established for each participating site and which will be used for all queries and query results.

Each data partner will execute the study query package locally and return results to the coordinating center for review and approval. Upon notification that the data partner is approved, they will receive the descriptive query package and return results which will be compiled into a report for the sponsor and be used to inform the study education and implementation plan.

Analyses of these data will be detailed in a separate statistical analysis plan. All query results will be published in a manuscript.

8.3 Cohort Identification Query Impact

The estimated 10 EHR sites that participate in the educational intervention study will be supplied with a cohort identification query. This query captures inclusion and exclusion criteria available in the EHR and returns a list of potentially eligible participants for further consideration. The query can be run as frequently as the participating site decides once it has been initially programmed and distributed.

9. Appendix 1: Regulatory, Ethical, and Study Oversight Considerations

9.1 Regulatory and Ethical Considerations

This study will be conducted in accordance with the protocol and with the following:

- Consensus ethical principles derived from international guidelines including the Declaration of Helsinki and Council for International Organizations of Medical Sciences (CIOMS) International Ethical Guidelines
- Applicable ICH Good Clinical Practice (GCP) Guidelines, where applicable
- Applicable laws and regulations

The protocol, protocol amendments, ICF, Investigator Brochure, and other relevant documents (e.g., advertisements) will be submitted to an IRB/IEC by the investigator and reviewed and approved by the IRB/IEC before the study is initiated.

Any amendments to the protocol will require IRB/IEC approval before implementation of changes made to the study design, except for changes necessary to eliminate an immediate hazard to study participants.

The investigator will be responsible for the following:

- Providing written summaries of the status of the study to the IRB/IEC annually or more frequently in accordance with the requirements, policies, and procedures established by the IRB/IEC
 - Notifying the IRB/IEC and the Funder, BI of SAEs or other significant safety findings as required by IRB/IEC procedures and in as described in section 1.2 of the protocol
- Providing oversight of the conduct of the study at the site and adherence to requirements of 21 CFR, ICH guidelines, the IRB/IEC, European regulation 536/2014 for clinical studies (if applicable), and all other applicable local regulations

9.2 Informed Consent Process

- The investigator or his/her representative will explain the nature of the study to the participant or his/her legally authorized representative and answer all questions regarding the study.
- Participants must be informed that their participation is voluntary. Participants or their legally authorized representative will be required to sign a statement of informed consent that meets the requirements of 21 CFR 50, local regulations, ICH guidelines, HIPAA (Health Insurance Portability and Accountability Act) requirements, where applicable, and the IRB/IEC or study center.
- The medical record must include a statement that written informed consent was obtained before the participant was enrolled in the study and the date the written consent was obtained. The authorized person obtaining the informed consent must also sign the ICF.
- A copy of the ICF(s) must be provided to the participant or the participant's legally authorized representative.

9.3 Data Protection

- Participants will be assigned a unique identifier by the sponsor. Any participant records or datasets that are transferred to the sponsor will contain the identifier only; participant names or any information which would make the participant identifiable will not be transferred.
- The participant must be informed that his/her personal study-related data will be used by the sponsor in accordance with local data protection law. The level of disclosure must also be explained to the participant.
- The participant must be informed that his/her medical records may be examined by Clinical Quality Assurance auditors or other authorized personnel appointed by the sponsor, by appropriate IRB/IEC members, and by inspectors from regulatory authorities.

COORDINATE-Diabetes is a prospective cluster-randomized clinical trial to test the effectiveness of an innovative, clinic-level educational intervention to improve the management of patients with Type 2 diabetes mellitus (T2DM) and cardiovascular disease (CVD). After IRB approval, sites will be randomized to a basic education arm or an intensive educational intervention arm, consisting of clinic-level multifaceted educational intervention aimed on improving evidenced-based care for patients with diabetes and cardiovascular disease. Site randomization will be stratified by Urban vs. non-urban. The aim is to enroll on average 30 patients at each site of 46 cardiology clinic centers (23 in each arm) in the United States.

1.1 Primary Objectives

To test effectiveness of implementing a clinic-level multifaceted intervention that includes establishing cardiology and endocrinology partnerships and evidence-based care pathways to improve the medical management and care of patients with T2DM and cardiovascular disease.

1.2 Site and Patient Inclusion Criteria

Sites will be recruited based on sufficient patient volume, cardiologist and endocrinologist or diabetes care specialist commitment, and site capacity to perform the trial as well as ability to effectively communicate with the study team and patients. Attempts will be made to achieve geographic, investigator, and patient diversity.

Individual patients eligible to enroll in the trial will have a diagnosis of T2DM and cardiovascular disease as listed in the Inclusion Criteria. Detailed patient inclusion and exclusion criteria are included in study protocol.

Site Inclusion Criteria:

1. Cardiology clinic that is willing and able to perform the interventions in the trial to improve the quality of care of their patients with T2DM and CVD
2. Have a cardiologist and endocrinologist or diabetes care specialist (for example, a PCP with experience in treating diabetes) who are willing to partner for the trial needs of creating and implementing care pathways with the support of the COORDINATE Diabetes Study Team; any site that has a highly organized partnership with cardiology-endocrinology with care pathways already established will not be included.

3. Presence of an electronic health record (EHR) system that will enable identification and follow-up of patients

1.3 Sample Size Justification

The primary outcome is the proportion of patients achieving guideline-recommended therapy, defined as a composite score of 3 at the last follow-up visit. The primary analysis is based on the comparison of primary outcome between the basic education and intensive educational intervention arms. The sample size provides adequate power to detect a clinically meaningful effect size of at least a 10% difference between treatment arms in the proportions of patients achieving a composite score of 3 by the last follow-up visit.

In this cluster-randomized trial, where the experimental unit is site, the effective sample size and power is impacted by intra-cluster correlation (ICC). For the primary outcome, the sample size calculation is based on the ability to detect at least a 10% difference between treatment arms in the proportion of patients achieving guideline-recommended management for T2DM and CVD with composite score of 3. The effect size of a 10% change has been chosen as a clinically meaningful difference between the intensive educational intervention and basic education arms.

A minimum of 42 sites (“clusters”) with an average cluster size of 25 patients per site (a total of 1050 patients) will provide at least 85% power to detect a 10% difference in the primary outcome between educational intervention arms through the last follow-up visit (6 to 12 months). This estimate of a minimum of 21 sites per arm (average of 25 patients per site) is based on the assumption of 10% of patients in the basic education arm, and at least 20% in the intensive educational intervention arm, receiving guideline-recommended therapy at the last follow-up visit, with an intra-correlation coefficient (ICC) of 0.05, and two-sided type I error rate of 0.05. The sample size/power calculations were carried-out using R function “n4props” in (package “CRT Size”).¹

2. General Considerations for Data Analysis

We will follow the guidance and standards for reporting of key elements based on the CONSORT statement for cluster randomized studies². Key elements will include the following items: descriptions of participants, interventions, objectives, outcomes, and sample size justification; and details about the randomization procedure, factors used to stratify randomization, (lack of) blinding, statistical methods, participant flow, dates of recruitment, baseline data by individuals and by cluster, numbers analyzed, outcomes and estimation, adverse events, and a discussion.

Trial population details, including the number of sites randomized, number of patients, median and range of number of patients across sites, the number of patients in intensive and basic arms,

and the number of patients lost to follow-up, withdrawn, or excluded from analyses will be presented in a flow diagram (Appendix 3. Figure 1).

All analyses will be conducted using SAS version 9.4 or higher software. All tests will be two-sided and a p-value of <0.05 will be considered statistically significant. As this is a cluster randomized trial, all p-values will account for site.

2.1 Analysis Datasets and Baseline Comparisons

Data from all enrolled patients will be included in the analysis. To be enrolled in the study, patients must meet trial inclusion and exclusion criteria as detailed in the protocol. Baseline comparisons of patient characteristics in each arm will be summarized as the mean (SD), median (25th, 75th percentiles) for continuous variables, and as counts (percentages) for categorical variables. Differences in baseline patient characteristics between randomized arms will be assessed at the patient-level using absolute standardized differences and at the site-level using Wilcoxon rank-sum test for continuous variables and the Pearson's chi-square test or the Fisher's exact test for categorical variables. All trial objectives will be analyzed using the intention-to-treat principle.

2.2 Missing Data

Operational efforts will be made to minimize missing data at baseline and during follow-up. Data quality checks will be built into the electric data capture system. Baseline and follow-up data will be reviewed on a regular basis and sites will be notified regarding any data quality concerns. DCRI study team will confirm with sites that missing data cannot be obtained. We anticipate negligible rates of missing data at baseline and follow-up as sites are conducting follow-up with their patients and electronic health system.

For the primary analysis, missing data for lab values and vital signs will be imputed to age and gender specific modes for categorical variables and medians for continuous variables. Missing data for medical history will be imputed to modes for categorical variables and medians for continuous variables. Missing medication data during follow-up will not be imputed, rather we will use a mixed-effects repeated measures model (MMRM) that effectively accounts for missing and correlated data within subject which is described in detail (Section 3.1)³. On indicated/guideline recommended therapy (yes/no) will be carried forward rather than the medication itself. Note, the intervention arm compared with usual care has additional follow-up at 3 and 9 months. This additional follow-up data will be used to help carry out the intervention through site audit and feedback reports, but will not be used as part of the primary outcome. Missing data may occur during follow-up due to a provider recommended temporary or permanent discontinuation of T2DM and CVD management in order to treat serious medical conditions, such

as leukemia. Rates of serious medical conditions should be similar by treatment arm. Missing data due to serious medical conditions will be treated the same as missing data for other known or unknown reasons. A sensitivity analysis will be conducted imputing missing last follow-up composite scores as failures. To better gauge the effect of truncating study follow-up time, we will conduct a sensitivity analysis that uses only 6-month outcome data.

3. Endpoints

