4.1 Basic Education Arm

Clinics in the basic education arm will continue current standard of care (SOC). Sites will be compensated for their involvement including for patient recruitment and assessments. They will also receive basic education at study start to include the most updated ACC/AHA guidelines for cholesterol management and from the ADA about diabetes management as well as periodic educational updates.^{2, 5, 6} They will also receive clinic-level education related to drug safety, including statin side effects and potential side effects of anti-diabetes medications with CV benefit (such as hypoglycemia, DKA, etc.). Beyond this basic information, sites (and physicians) in the basic education arm will not receive other instructions or intensive educational interventions. They will be left to care for their patients as they normally would. Patients in the basic education arm will be seen by their healthcare provider at baseline, either in clinic or via virtual visit, per local standard of care. Follow-up visits (i.e., standard of care in-person or virtual visit, or telephone call) will be conducted by enrolling sites in the basic arm at 6 months from baseline visit, and at up to 12 months from baseline visit, with a maximum of two visits. The overall length of follow-up will be 6 to 12 months, with all patients having a minimum of 6 months of follow-up. The date of the last follow-up visit determined by the patient's enrollment date. Data collected will be entered into an electronic data capture system. Clinic visits should be conducted as per standard of care.

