- Clinic visits: Patients in the intense intervention arm will be seen by their healthcare provider at baseline, either in clinic or via virtual visit, per local standard of care. Follow-up visits (i.e., standard of care in-person or virtual visit, or telephone call) will be conducted every three months by enrolling sites in the intervention arm. All patients in the intervention arm will have two to four follow-up visits, with a minimum of 6 months of follow-up. The overall length of follow-up will be 6 to 12 months. The date of the last follow-up visit will

be determined by the patient's enrollment date. Patient reported prescription data for medications of interest will be validated by sites via medical record collection. All data collected will be entered into an electronic data capture system. Clinic visits should be conducted as per standard of care.

• Labs: The following laboratory assessments are collected from the patient's electronic health record and are recommended as part of standard of care in all patients at baseline and at the last follow-up visit: basic metabolic panel, HbA1c, lipid panel. As part of standard of care, providers will be encouraged to also order a basic metabolic panel 1-2 weeks after each dosage change in ACEi/ARB, HbA1c every 3 months until it is <8%, and lipid panel 8 weeks after each statin dose titration. In summary, sites will be educated to guidelines and will not be mandated to collect specific labs at specific times from patients enrolled for the purpose of the study. Rather, the study will be collecting data including labs that have been performed as part of standard of care and are not required as part of the study.

In both study arms, we will evaluate and compare various methods to communicate with and engage patients throughout the study. These engagement efforts may focus on encouraging the patients to enroll/comply with study requirements, and/or may focus on encouraging the patient to be engaged in their own health care, knowledgeable about their disease state(s), and adherent to their medications.

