4.3 Study Duration

Follow-up for the overall study will end approximately 6 months after enrollment of the final participant. Participants will be followed for 12 months, except for those enrolled in the final 6 months of enrollment, who will have their follow-up complete at a minimum of 6 months. Thus, the last patient enrolled will have 6 months of follow-up, a patient enrolled 3 months before the end of enrollment will have 9 months of follow-up, and a patient enrolled 6 months before the end of enrollment will have 12 months of follow-up. Shortly following the completion of enrollment, study sites will be notified of a specific date on which follow-up will conclude.

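### SAP 2.2 bars the intensive arm's 9-month contact from the primary outcome even when it is the patient's last follow-up visit, and the basic arm's closing visit has no matching bar

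*SAP*

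**What the plan says.** **Outcome.** Protocol 1.2 and 7.3 and SAP 1.3 and 3.1 all place the primary outcome at the last follow-up visit.

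**Length of follow-up.** Patients enrolled in the final six months are followed for less than 12 months. Protocol 4.3 gives the example that "a patient enrolled 3 months before the end of enrollment will have 9 months of follow-up". This applies to both arms.

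**Visits, basic arm.** Protocol 4.1 schedules follow-up "at 6 months from baseline visit, and at up to 12 months from baseline visit, with a maximum of two visits".

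**Visits, intensive arm.** Contacts are every three months, and Protocol 4.2 states that "All patients in the intervention arm will have two to four follow-up visits". Table 3 gives the 9-month contact a window of months 8 to 10 and the 12-month contact a window of months 11 to 13. The 9-month column holds medications and vital status. HbA1c, LDL-C and vital signs appear only at baseline and in the 12-month column.

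**Exclusion.** SAP 2.2 notes that the intervention arm has extra contacts at 3 and 9 months and says that these data serve audit and feedback "but will not be used as part of the primary outcome".

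**Model and sensitivity analyses.** SAP 3.1 plans a repeated-measures logistic model with categorical time and a treatment-by-time interaction. It lists neither the time levels nor the contrast that gives the primary odds ratio. SAP 2.2 plans one sensitivity analysis that counts missing final scores as failures and another that uses 6-month data only.

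**The concern.** Take two patients enrolled three months before enrolment closes, one in each arm. Both are followed for 9 months. The intensive-arm patient is contacted at months 3, 6 and 9, so the 9-month contact is the last visit, and SAP 2.2 removes it. The basic-arm patient has a 6-month visit and a closing visit near month 9, and nothing in the SAP removes that. The exclusion attaches to contacts that exist in one arm only, so declaring that everyone is scored at last follow-up does not cure the conflict while the exclusion stands.

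Three things are at stake. The time of assessment, or the amount of missing data, could differ by arm by design. The failure-imputation sensitivity analysis could penalise one arm for data that were in fact collected. And in an open-label trial the choice of reading would fall to the analyst.

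**Working it through.** **1. The plan's own power figure.** From SAP 1.3: 21 sites per arm, 25 patients per site, 10% against 20%, "intra-correlation coefficient (ICC) of 0.05, and two-sided type I error rate of 0.05".
- Design effect = 1 + (25 − 1) × 0.05 = 2.2.
- Effective n per arm = 21 × 25 / 2.2 = 238.6.
- Power: 86.7% (normal, pooled variance), 87.1% (unpooled), 85.4% (t with 40 df).

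The claim that the design "will provide at least 85% power to detect a 10% difference in the primary outcome" is reproduced and is not in dispute. The figures below use the pooled formula, so their reference is 86.7%.

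**2. Share of patients affected.** The documents do not give the length of enrolment. Assume uniform enrolment over E months. Follow-up lasts 12 months for a fraction (E − 6)/E and is spread evenly over 6 to 12 months for the rest. Follow-up ends inside Table 3's 8-to-10-month window for a fraction 2/E.

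**3. Illustration A: the barred patients are read at 6 months in the intensive arm only.** Assume also that response is proportional to follow-up time and that 20% is the intensive-arm rate when everyone is read at true last follow-up. Mean follow-up is [12(E − 6) + 9 × 6]/E. Affected patients are read on average 3 months early, so loss = (2/E) × 3 / mean follow-up × 20 points.

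| E (months) | Affected | Mean follow-up | Loss (points) | Power |
|---|---|---|---|---|
| 12 | 16.7% | 10.5 | 0.95 | 80.3% |
| 18 | 11.1% | 11.0 | 0.61 | 82.8% |
| 24 | 8.3% | 11.25 | 0.44 | 83.9% |
| 30 | 6.7% | 11.4 | 0.35 | 84.5% |

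The result depends a little on the time to which the 20% refers. If it is a 12-month rate, the divisor is 12: loss 0.83 to 0.33, power 81.2% to 84.6%. If it is the affected patients' own rate at 9 months, the divisor is 9: loss 1.11 to 0.44, power 79.1% to 83.9%. Overall: 0.3 to 1.1 points, power 79.1% to 84.6%.

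**4. Illustration B: the barred patients are missing at the late time level, and the contrast is at that level.** The basic arm's late level then includes 8-to-10-month readings and the intensive arm's does not. Place every closing visit from month 10 at the late level in both arms.
- E = 12: mean follow-up is (0.5 × 12 + 0.333 × 10)/0.833 = 11.2 months in the basic arm and (0.5 × 12 + 0.167 × 11)/0.667 = 11.75 in the intensive arm. If 10% is the basic rate at 11.75 months, it reads 10 × 11.2/11.75 = 9.5%.
- E = 30: 11.71 against 11.92 months, so 9.8%.

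Here the basic arm is lowered by 0.2 to 0.5 points, which favours the intervention. The sign is the reverse of illustration A.

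**5. Failure imputation.** If a barred 9-month score counts as missing, and affected patients respond at the average rate, the intensive-arm rate becomes 20 × (1 − 0.167) = 16.7% for E = 12 and 20 × (1 − 0.067) = 18.7% for E = 30. The basic arm would not change.

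**6. The larger enrolment aim.** The SAP introduction aims for 46 sites of 30 patients. The design effect is then 2.45, effective n per arm is 23 × 30/2.45 = 281.6, and power is 91.6%. With the largest loss in step 3 (1.11 points) it is 85.3%. The power cost would thus bring the trial below its stated figure at the minimum size, but not at that aim.

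**The case against.** A reader might infer that the intensive-arm patient is scored at 6 months, the matching basic-arm patient at about 9 months, and that the comparison is therefore biased against the intervention. The documents do not support that as fact, for four reasons.

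- SAP 3.1, in fixing which drug list applies, describes last follow-up as month 6 or month 12 without separating the arms. Applied evenly, both closing visits fall back to month 6 or both count as the final visit.
- SAP 2.2 excludes follow-up that is additional to usual care. A closing visit that both arms receive is arguably not additional. Placing labs only in the 12-month column, while SAP 3.2.2 analyses them at last follow-up, suggests that the 12-month form may serve as the end-of-study form.
- In a model with categorical time, a patient without a late record contributes the 6-month record and is missing later. The patient is not re-scored at 6 months.
- The direction can reverse, as step 4 shows.

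The 6-month-only sensitivity analysis also treats the arms alike.

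All of this limits the claim, but none of it supplies the missing rule. The month-6-or-12 wording does not say where a 9-month closing visit goes, and Table 3's 12-month window does not reach back to month 9. SAP 2.2 also muddies the missing-data reading: it says follow-up medication data are not imputed, then speaks of carrying therapy status forward. The 6-month sensitivity analysis answers a shorter question and does not define the primary analysis.

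**Conclusion.** The conflict is in the text. A stated exclusion that applies to one arm removes what Protocol 4.2 and 4.3 make the last follow-up visit for some intensive-arm patients, and the basic arm's closing visit has no matching exclusion. Arm-symmetric readings are possible but none is written down, so the plan can give an arm-dependent result and should be corrected.

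The size is modest. About 7% to 17% of patients are affected, with a shift of roughly 0.3 to 1.1 points and power of roughly 79% to 84.6% at the minimum sample size. These figures are illustrative: they rest on uniform enrolment over an assumed 12 to 30 months, response proportional to follow-up time, the 8-to-10-month window, and a 6-month reading in the intensive arm only. They do not show that the primary result will be biased, or in which direction. The clearest one-sided risk is the failure-imputation analysis, where only the intensive arm could lose successes.

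**What to change.** Amend SAP 2.2 and 3.1 before database lock.

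- **Closing contact.** The contact at the end of a patient's follow-up is the last follow-up visit for the primary outcome in both arms. It has the same window and is mapped to the same analysis time level in both. Three-month contacts, and 9-month contacts followed by a later visit, stay excluded. State the lower boundary of the late level; month 8, where Table 3's 9-month window opens, would fit, with earlier closing contacts placed at the 6-month level in both arms.
- **HbA1c.** For the metformin alternative, use the most recent chart value at the closing contact in both arms. SAP 3.1 says HbA1c is collected only at baseline and 12 months, so a 9-month closing contact would otherwise be unable to score a follow-up value.
- **Contrast.** List the levels of time in the model and state which contrast gives the primary odds ratio.
- **Failure imputation.** Define a missing final score by the same rule, so that a collected closing score is never counted as a failure.
- **Protocol and Table 3.** Align 4.1, 4.2 and Table 3 on the closing contact and its window.

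The cost is a few sentences. The medication record check is already collected at 9 months in the intensive arm, so no new medication data are needed there; the HbA1c look-up is an added chart item for these patients. The late level will mix follow-up of about 8 to 13 months, equally in both arms. Keep the 6-month-only analysis as a check on that.
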